7.5.2. Data collection procedures for adverse events

Participants will be interviewed regarding medical conditions, medication changes, and symptoms that have occurred at each study visit. An Adverse Event form will be completed if any adverse event is reported. If the study coordinator or a study physician learns of any hospitalizations or other adverse events between study visits, an Adverse Event form will be completed. All adverse events and Serious Adverse Events from time of study entry (consent) up to the end of follow-up (week 96) will be reported to the DCC.

A Serious Adverse Event form will be completed for all adverse events rated as serious.

Participants will be followed for all ongoing unresolved adverse events until they are either resolved, or in the opinion of the study physician, the participant is medically stable.

A study physician will assess the relationship of each adverse event to the use of study drug, based on available information, using guidelines outlined in the MOP.

7.5.3 Reporting procedures

All serious adverse events that are unexpected and related to study drug(s) will be reported to the DCC within 24 hours of knowledge of the event, via the Serious Adverse Event form. This reporting includes serious adverse events that occur from the time the participant has signed the clinical trial consent.

The DCC will distribute the expedited report to the NIDDK, the appropriate oversight committees or entities, and clinical centers. Status reports on serious adverse events will be generated by the DCC and will include the relationship of the adverse event to trial medications, the severity of the event and if the event is resolved or ongoing.

All deaths will be reported to the DCC within 24 hours of knowledge of the death via the Serious Adverse Event form. This reporting begins at the time the participant has signed the informed consent up to the last scheduled participant visit. The report will include the relationship of the death to trial medications. A Clinical Outcome form will also be completed and sent to DCC for distribution. Deaths will be reported immediately to the NIDDK, the appropriate oversight committees or entities, and the clinical centers. A death will be reported as an expedited report only if it is unexpected and drug related. A death must also be reported in accordance with local law and regulations.

The HBRN will comply with Genentech/Roche and Bristol-Myers Squibb SAE reporting requirements (see Manual of Operations).

7.5.4. Management if either entecavir or peginterferon alfa-2a is discontinued due to adverse events

If entecavir is discontinued due to adverse event, then peginterferon alfa-2a will be continued until the end of the treatment period. If peginterferon alfa-2a is discontinued due to adverse

event, then entecavir will be continued until the end of the treatment period.

8. Statistical considerations

8.1. Statistical analysis

Summary statistics will be generated to describe the study sample at baseline. Descriptive statistics, including measures of central tendency (e.g. means, medians) and estimates of spread (e.g., standard deviations, quartiles) will be used for continuous variables such as age and baseline HBV DNA and HBsAg levels. Frequency distributions will be used for categorical variables such as HBV genotype and HBeAg status. Ninety-five percent confidence intervals will be calculated for all point estimates of continuous data. Graphical displays (e.g. histograms, box plots) will also be used to describe the data.

8.1.1. Analysis of primary endpoints

The primary endpoints include safety, measured by the rate of adverse and Serious Adverse Events, and efficacy, defined as loss of HBeAg and HBV DNA $\leq 1,000$ IU/mL at the end of follow-up (week 96). That is, only participants achieving HBeAg loss and having HBV DNA ≤ 1000 IU/mL at the end of follow-up will be considered as achieving the primary efficacy endpoint.

Safety

Summaries of adverse events (number of adverse events, number and percentage of participants with at least one adverse event, and for each adverse event, rate per person-years) will be provided. Events will be summarized based on the date of onset for the event. A treatment emergent adverse event will be defined as an adverse event that begins on or after the date of first dose of study drug.

Summaries of the following are planned:

- all adverse events recorded between screening and first dose of study medication,
- all treatment emergent adverse events,
- all emergent and related adverse events,
- all treatment emergent renal adverse events,
- all treatment emergent and related renal adverse events
- combined Grade 2, 3 and 4 treatment emergent adverse events,
- combined Grade 2, 3 and 4 related treatment and emergent adverse events,
- combined Grade 3 and 4 treatment emergent adverse events,
- combined Grade 3 and 4 related treatment and emergent adverse events,
- all adverse events that caused permanent discontinuation of study drug,
- all adverse events that caused temporary interruption of study drug,
- all serious adverse events, and
- all serious and related adverse events.

We will provide 95% confidence intervals for the rate of adverse and serious adverse events.

Efficacy

The percentage of participants achieving the primary efficacy endpoint will be summarized with the point estimate and 95% confidence interval.

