Combination Entecavir and Peginterferon alfa-2a Therapy in HBeAg-Positive Immune Tolerant Adults with Chronic Hepatitis B

Synopsis

Study aims:

- To determine the safety and efficacy of treatment with 8 weeks of entecavir followed by 40 weeks of both entecavir and peginterferon alfa-2a in the treatment of chronic hepatitis B in HBeAg positive adults who are in the immune tolerant phase.
- To evaluate “off treatment” sustained responses after treatment with entecavir and peginterferon alfa-2a in the treatment of chronic hepatitis B in HBeAg positive adults who are in the immune tolerant phase.

Type of study

- Single arm treatment study

Clinical trial

A single arm pilot study of 8 weeks of entecavir followed by 40 weeks of both entecavir and peginterferon alfa-2a in adults with HBeAg-positive chronic hepatitis B with normal or near normal ALT levels and high serum levels of HBV DNA (“immune tolerant” HBeAg-positive chronic hepatitis B). All participants will be followed until week 96 (48 weeks after discontinuation of therapy) at which time the primary outcome will be measured.

1. Background

1.1. “Immune tolerant” HBV in adults

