1.3 Considerations in the treatment of immune-tolerant adults

There are no prior studies of treatment of immune tolerant adults. Data from the pediatric literature indicated that treatment with IFN alone during the immune tolerant phase of infection is rarely effective and loss of HBV DNA or anti-HBe seroconversion, with less than 10% of treated children achieving this outcome (12). However, the combination of a nucleoside analogue and IFN was examined in a pilot study of 23 children and appears encouraging (13). Lamivudine was given for 8 weeks and then combined IFN and lamivudine therapy for a further 44 weeks. HBV DNA by PCR was negative in 48% at end of treatment, and 5 (22%) children seroconverted to anti-HBe. Four (17%) children cleared HBsAg and seroconverted to anti-HBs. Six months after treatment, HBV DNA was again positive in all but the children who had seroconverted to anti-HBe and (presumably) anti-HBs.

Based upon these stimulating results, we propose to evaluate the safety and efficacy of a short lead-in course (8 weeks) of entecavir followed by combination of entecavir plus peginterferon alfa-2a for 40 weeks. We hypothesize that using a potent nucleos(t)ide analogue will provide a higher rate of HBeAg loss and suppression of HBV DNA. The primary measure of outcome will be HBeAg loss and suppression of HBV DNA to ≤ 1000 IU/mL in serum 48 weeks after stopping all antiviral therapy (sustained off-treatment response).

2. Study objectives

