2.2 Primary endpoint

2.2.1 Safety: Adverse Events and Serious Adverse Events through the end of treatment and through the end of follow-up

2.2.2 Efficacy: HBeAg loss (lack of detectable HBeAg) AND HBV DNA $\leq 1,000$ IU/mL 48 weeks after stopping therapy.

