2.3.2. Sustained end of follow-up responses 48 weeks after end-of-treatment (week 96)

- a. Cumulative HBsAg loss
- b. HBeAg loss
- c. HBeAg seroconversion
- d. HBsAg seroconversion
- e. ALT <45 U/L for men, <30 U/L for women (approximately 1.5 ULN)
- f. ALT normalization (men <30 U/L, women <20 U/L)
- g. HBV DNA ≤1000 IU/mL
- h. HBV DNA <20 IU/mL (LLOQ of COBAS Ampliprep/COBAS TaqMan HBV v2.0 test)

3. Study design

A single arm pilot study of 8 weeks of entecavir followed by 40 weeks of both entecavir and peginterferon alfa-2a in adults with HBeAg-positive chronic hepatitis B with normal or near normal ALT levels and high serum levels of HBV DNA ("immune tolerant" HBeAg-positive chronic hepatitis B). Participants will be followed until week 96 (48 weeks after discontinuation of therapy). Screening can include historical values up to 52 weeks prior to the baseline visit, but there must be a screening visit within 6 weeks of the baseline visit.

4. Study population

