6.11 Management algorithm for participants with ALT flare during the treatment phase

6.11.1. If ALT values increase to ≥ 300 U/L for males and ≥ 200 U/L for females, retest the hepatic panel within 4 weeks. Continue testing of hepatic panel every 4 weeks as long as the ALT remains >300 U/L for males and >200 U/L for females.

6.11.2. If ALT values decline below these levels, the frequency of testing the hepatic panel can return to the usual schedule.

6.11.3. Participants will remain on treatment until week 48 unless:

- i. there are signs of clinical decompensation or
- ii. total bilirubin ≥ 2.0 mg/dL and direct bilirubin ≥ 1.0 mg/dL or
- iii. ALT >450 U/L for males or >300 U/L for females for more than 12 weeks

Participants meeting any of these criteria will continue to be followed in the study but with any subsequent management at the discretion of the study physician.

6.12. Management algorithm for participants with ALT elevation during the follow-up phase (weeks 48-96)

6.12.1. If ALT increases to >300 U/L for males and >200 U/L for females, retest the hepatic panel in 4 weeks. Continue testing of hepatic panel every 4 weeks as long as the ALT >300 U/L for males and >200 U/L for females.

6.12.2. If ALT decline below these levels, the frequency of testing the hepatic panel can return to the usual schedule.

6.12.3. For participants with ALT persistently >150 U/L in males and >100 U/L in females for ≥ 24 weeks and HBV DNA $\geq 10,000$ IU/mL, they are eligible for retreatment with entecavir (up to one year or by December 31, 2015 (whichever comes first), or peginterferon alfa-2a or both drugs for one year if desired by participants and provider.

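### The Section 8.1.1 responder rule omits the off-treatment condition, so a participant suppressed on retreatment at week 96 could be counted as an off-treatment responder

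*Combined protocol and SAP*

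**What the plan says.** **Intent.** Section 1.3 sets the primary measure at "48 weeks after stopping all antiviral therapy (sustained off-treatment response"). Section 2.2.2 times it at "48 weeks after stopping therapy". The synopsis adds: "All participants will be followed until week 96 (48 weeks after discontinuation of therapy) at which time the primary outcome will be measured".

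**Scoring rule.** Section 8.1.1 gives "efficacy, defined as loss of HBeAg and HBV DNA" at or below 1,000 IU/mL at week 96, then adds that "only participants achieving HBeAg loss and having HBV DNA ≤ 1000 IU/mL at the end of follow-up will be considered as achieving the primary" … Neither sentence mentions treatment status.

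**Retreatment.** Section 6.12 covers ALT elevation in weeks 48–96. Under 6.12.3, participants qualify when ALT has stayed above 150 U/L (men) or 100 U/L (women) for at least 24 weeks and HBV DNA is at least 10,000 IU/mL. In that case "they are eligible for retreatment with entecavir (up to one year" or until 31 December 2015 if sooner), "or peginterferon alfa-2a or both drugs for one year if desired by participants and provider".

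**Failure rules.** Section 8.2 treats participants without week-96 endpoint data as failures. Sections 6.9 and 6.10 call primary non-response and virologic breakthrough treatment failures. No section classifies a retreated participant.

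**Secondary endpoints.** Section 2.3.2 is headed "Sustained end of follow-up responses 48 weeks after end-of-treatment (week 96") and lists items a–h. Section 8.1.2.2 reports them as frequencies and percentages with 95% intervals, again with no condition on treatment status.

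**The concern.** The endpoint is described as off-treatment in one place and scored in another by two laboratory values and a visit date. Between those two points the protocol allows the same drugs to be given again. A participant who relapses, is retreated and attends week 96 has endpoint data, so the missing-data rule does not apply and 8.1.1 scores the on-drug values.

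The efficacy result is a single-arm proportion with no comparator. Compared with scoring retreated participants as non-responders, the present rule can only raise that proportion. The participants affected are those whose ALT and HBV DNA were raised after treatment, which is the opposite of a sustained response. There is no hypothesis test, so what is at stake is the estimate and its label, not a decision rule.

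**Working it through.** **1. The plan's own precision table (Section 8.3).** Inputs: n = 40, two-sided 95% Clopper-Pearson limits. For x responders, lower = 0.025 quantile of Beta(x, n − x + 1) and upper = 0.975 quantile of Beta(x + 1, n − x).

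| Rate | x/40 | Plan | Recomputed |
|---|---|---|---|
| 0.15 | 6 | 0.057–0.298 | 0.0571–0.2984 |
| 0.20 | 8 | 0.091–0.356 | 0.0905–0.3565 |
| 0.25 | 10 | 0.127–0.412 | 0.1269–0.4120 |
| 0.30 | 12 | 0.166–0.465 | 0.1656–0.4653 |

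The table reproduces to rounding.

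**2. Can retreatment fall before week 96?** The 6.12 heading limits the section to weeks 48–96, so take the 24 weeks of raised ALT from week 48.
- Earliest eligibility: 48 + 24 = week 72. Longest retreatment by week 96: 96 − 72 = 24 weeks.
- If ALT is first raised at week 52: 52 + 24 = week 76, leaving 96 − 76 = 20 weeks.
- Section 6.6 schedules visits at weeks 52, 60, 72 and 96 only. Section 6.12.1 adds four-weekly panels only above 300 U/L (men) or 200 U/L (women). Below those levels, scheduled visits show 24 weeks of elevation before week 96 only if ALT was already raised at week 48 (48 to 72). From week 52 or 60, the next scheduled visit at least 24 weeks later is week 96 itself.

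The window exists but is narrow.

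**3. Can the HBV DNA limit be met on drug?** At the minimum trigger the fall needed is log10(10,000/1,000) = 1 log10. A participant back at the entry level of 10⁷ IU/mL would need log10(10⁷/10³) = 4 log10. Section 5.2.2 cites a mean fall of 2.8 logs over 28 days on entecavir, and Section 5.2.1 cites 5–6 logs in treatment-naïve patients. Retreated participants are not treatment-naïve, so these figures are only a guide, but the limit is plausibly reachable. HBeAg loss is the restrictive component.

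**4. Size for the primary endpoint.** Each case is 1/40 = 2.5 percentage points. If one apparent responder had been retreated:

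| Scored by 8.1.1 as written | Retreated participant scored as non-responder |
|---|---|
| 6/40 = 15.0% (5.7–29.8) | 5/40 = 12.5% (4.2–26.8) |
| 8/40 = 20.0% (9.1–35.6) | 7/40 = 17.5% (7.3–32.8) |
| 10/40 = 25.0% (12.7–41.2) | 9/40 = 22.5% (10.8–38.5) |
| 12/40 = 30.0% (16.6–46.5) | 11/40 = 27.5% (14.6–43.9) |

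With no case, nothing changes.

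**5. Secondary endpoints.** Items e–h of 2.3.2 need only an ALT or HBV DNA threshold, so on-drug suppression can meet them without HBeAg loss. Items a–d (HBsAg and HBeAg loss and seroconversion) are harder to reach but carry the same sustained label. With 40 in the denominator, each case again adds 2.5 points; the number of cases cannot be derived from the documents.

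**The case against.** **The endpoint is already defined as off-treatment.** Someone on retreatment at week 96 is not 48 weeks past stopping all antiviral therapy, so 1.3 excludes the case, and 8.1.1 analyses that same endpoint. The sentence beginning with *only* can also be read as a necessary condition. This stands in part: a reader might infer that the plan has no off-treatment intent, and 1.3 and 2.2.2 show otherwise. But the sentence just before it in 8.1.1 is definitional and complete without the condition, and 2.2.2 is less explicit than 1.3.

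**Other failure rules may catch these participants.** The definition of breakthrough in 6.10 has no time limit. A participant who was below 1,000 IU/mL and reaches 10,000 IU/mL has risen by more than 1 log10, which, if confirmed, could count as breakthrough and so as treatment failure. It would therefore be wrong to say that 8.2 holds the only failure rule. However, the steps in 6.9 and 6.10 are to reinforce compliance, stop study treatment and follow up after discontinuation, which points to on-treatment use. Neither section classifies retreatment, and 8.1.1 does not refer to them.

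**Time on retreatment.** A reader might infer up to 96 − 48 = 48 weeks, by counting ALT raised before week 48. The 6.12 heading favours counting from week 48, so about 24 weeks is the supportable maximum.

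**The effect is small.** This stands for the primary endpoint: a shift of 2.5 points sits inside an interval about 29 points wide, in a pilot without a test. It makes the correction minor but does not make the rule correct.

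**Conclusion.** Wrong as written. Applied literally, 8.1.1 can score on-drug suppression as the off-treatment response described in 1.3 and 2.2.2, and 8.1.2.2 has the same gap for 2.3.2 a–h.

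The likely effect on the primary endpoint is 0 or 1 participant, or 0 to 2.5 points. That is an assumption, since no retreatment rate is given. It rests on how much must coincide: 24 weeks of raised ALT, HBV DNA of at least 10,000 IU/mL, optional retreatment actually taken, HBeAg loss, and HBV DNA back to 1,000 IU/mL or less, within about 24 weeks. Items e–h could be affected more often.

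A reader might infer that the primary result will be materially inflated. The documents do not support that. They show that the rule permits the error, not that it will occur often.

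**What to change.** In 8.1.1 and 8.1.2.2, state that a participant who starts any therapy given to treat hepatitis B after the initial study course and before the week-96 assessment is a non-responder for the primary endpoint and for all the sustained endpoints in 2.3.2 (a–h). For cumulative HBsAg loss, only losses after retreatment starts are not counted; earlier losses stand. Brief, episodic famciclovir or valacyclovir for herpes, which exclusion criterion 4 already tolerates, does not count as such therapy.

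Identify these participants from the concomitant-medication record taken at each visit (Section 5.5), and report how many were retreated. An analysis of observed week-96 values regardless of retreatment is an optional sensitivity analysis.

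The cost is a few sentences of analysis text. Sample size, visits and data collection stay the same, and eligibility for retreatment under 6.12.3 is unchanged. The downside is that reported response rates may fall slightly.

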2.1 Primary objectives

- To determine the safety and efficacy of treatment with 8 weeks of entecavir followed by 40 weeks of both entecavir and peginterferon alfa-2a in the treatment of chronic hepatitis B in HBeAg positive adults who are in the immune tolerant phase.
- To evaluate “off treatment” safety and sustained responses after treatment with entecavir and peginterferon alfa-2a in the treatment of chronic hepatitis B in HBeAg positive adults who are in the immune tolerant phase.

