6.4. On-treatment assessments

After starting treatment, visits will occur at weeks 8, 12, 16, 20, 24, 30, 36, 42, and 48. Each visit will include assessment of compliance, adverse events reporting, vital signs, weight, symptoms evaluation, record of concomitant medications, and blood testing as detailed in Schedule of Events (Appendix I). Participants will be dispensed study medications.

1. At the Week 8 visit, peginterferon alfa-2a will be provided to subjects with instructions on its use, including education on self-injection, if appropriate. Subjects will have a limited clinical evaluation as well as blood and urine tests.

2. Pregnancy test will be done in women with reproductive potential at each visit until the end of treatment.
3. Depression assessment will occur at weeks 8, 12, 24, 36 and 48.
4. QOL assessments will occur at day 0, weeks 8 and 48. Health behaviors will be included at day 0 and week 48.
5. Fatigue questionnaire will occur at day 0.
6. CBC (with differential), hepatic panel (ALT, AST, total bilirubin), renal panel (Cr, CrCl) and HBV DNA quantitation at each visit.
7. TSH at week 12, 24, 36 and 48.
8. Albumin, alkaline phosphatase, glucose and total protein will be obtained at week 48
9. HBeAg at weeks 8, 12, 24, 36 and 48.
10. HBsAg at week 48.
11. Blood samples for serum/plasma at each visit.
12. HBsAg and HBeAg quantification at each visit.
13. Anti-HBs/HBe will be done at day 0 and week 48. Also at the next visit if HBsAg/HBeAg becomes negative.

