6.6. Post-treatment assessments

1. Visits will occur at weeks 52, 60, 72, and 96 .
2. Depression assessment will occur at weeks 60 and 96.
3. QOL and health behaviors assessments will occur at week 96.
4. Fatigue questionnaire will be obtained at week 96.
5. CBC (without differential), hepatic panel (ALT, AST, total bilirubin), renal panel (Cr, CrCl), and HBV DNA quantitation at each visit.
6. TSH at week 60.
7. Albumin, alkaline phosphatase, total protein, glucose, INR/PT, and urinalysis at week 96.
8. HBeAg at weeks 60, 72, and 96.
9. HBsAg at weeks 72 and 96.
10. HBsAg and HBeAg quantification every visit.
11. Blood samples for serum/plasma at each visit.
12. Anti-HBs/HBe will be done at week 96. Also at the next visit if HBsAg/HBeAg becomes negative.

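### After week 60 silent ALT flares are less likely to be detected than on treatment, so their rate per person-year in section 8.1.1 is biased downward relative to the on-treatment period

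*Combined protocol and SAP*

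**What the plan says.** Section 8.1.1 summarises adverse events as counts, as participants with at least one event and, "for each adverse event, rate per person-years", with 95% confidence intervals. Section 2.2.1 sets the safety endpoint as "Adverse Events and Serious Adverse Events through the end of treatment and through the end of follow-up", and section 2.1 makes off-treatment safety part of a primary objective: "To evaluate “off treatment” safety and sustained responses after treatment with entecavir and peginterferon alfa-2a".

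The testing schedule differs between the two halves of the study. On treatment (section 6.4), "visits will occur at weeks 8, 12, 16, 20, 24, 30, 36, 42, and 48", with "CBC (with differential), hepatic panel (ALT, AST, total bilirubin), renal panel (Cr, CrCl) and HBV DNA quantitation at each visit". After treatment (section 6.6), "Visits will occur at weeks 52, 60, 72, and 96", with "CBC (without differential), hepatic panel (ALT, AST, total bilirubin), renal panel (Cr, CrCl), and HBV DNA quantitation at each visit". The schedule of events in Appendix I agrees. Denser testing off treatment depends on a finding already made (section 6.12.1): "If ALT increases to >300 U/L for males and >200 U/L for females, retest the hepatic panel in 4 weeks". The on-treatment rule in section 6.11.1 works in the same way.

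The statistical section does not mention the unequal test intervals.

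**The concern.** A rate per person-year treats each week of follow-up as equally able to reveal an event. That is reasonable for events that participants feel and report. It is not reasonable for an ALT rise without symptoms, which is seen only if blood is drawn while it lasts. Section 7.3.1 lists hepatitis flares and liver enzyme changes among the adverse effects of entecavir, and section 7.5.1 defines an adverse event broadly enough to include them.

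Off-treatment safety would then be read partly from a period in which short silent flares are more easily missed. The planned confidence intervals cover sampling error, not missed events. Splitting the person-time into on- and off-treatment parts would not remove the problem, because the missed events lie within the off-treatment part. Section 8.1.1 also places events by date of onset, and for a silent flare first seen at week 96 the onset is known only to within 24 weeks.

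**Working it through.** **The plan's own figures.** The plan states no flare rate or adverse event rate, so there is none to reproduce on this point. Its only calculated figures, the Clopper-Pearson widths in section 8.3 (0.24, 0.27, 0.29, 0.30), reproduce at n = 40 as 0.241, 0.266, 0.285 and 0.300. They concern efficacy.

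**Inputs from the documents.**
- On-treatment gaps between panels (section 6.4, from day 0): 8, 4, 4, 4, 4, 6, 6, 6, 6 weeks. That is 9 panels in 48 weeks, mean gap 48/9 = 5.3 weeks.
- Off-treatment gaps (section 6.6, from week 48): 4, 8, 12, 24 weeks. That is 4 panels in 48 weeks, mean gap 48/4 = 12 weeks.

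**Assumptions, not in the documents.** The flare is silent, lasts D weeks, and starts at a uniformly distributed time within the period. D is varied because no duration is given.

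**Formula.** A flare is caught if a scheduled panel falls within it, so the share detected is the sum over gaps of min(gap, D), divided by the length of the period.

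| D (weeks) | Weeks 0-48 | Weeks 48-96 | Off/on detection | True off/on rate ratio at which observed rates look equal |
|---|---|---|---|---|
| 4 | 36/48 = 75% | 16/48 = 33% | 0.44 | 2.25 |
| 8 | 48/48 = 100% | 28/48 = 58% | 0.58 | 1.71 |
| 12 | 48/48 = 100% | 36/48 = 75% | 0.75 | 1.33 |
| 16 | 48/48 = 100% | 40/48 = 83% | 0.83 | 1.20 |
| 24 or more | 48/48 = 100% | 48/48 = 100% | 1.00 | 1.00 |

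**Where the loss lies.** In weeks 48-60 (gaps 4 and 8), detection is 8/12 = 67% for a 4-week flare and 12/12 = 100% for an 8-week flare, close to the on-treatment figures. In weeks 60-96 (gaps 12 and 24), it is 8/36 = 22%, 16/36 = 44% and 24/36 = 67% for flares of 4, 8 and 12 weeks.

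**Cumulative windows of section 2.2.1.** At equal true rates, the rate through week 96 divided by the rate through week 48 is:
- D = 4: (52/96)/(36/48) = 0.72
- D = 8: (76/96)/(48/48) = 0.79
- D = 12: (84/96)/(48/48) = 0.88

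**Sensitivity to fixed durations.** With exponential durations of mean m, the share detected is the sum of m(1 − exp(−gap/m)) over the gaps, divided by 48. The off/on ratio is then 0.53, 0.64, 0.71 and 0.82 for means of 4, 8, 12 and 24 weeks. The direction is the same.

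**What would be observed.** Take an assumed true on-treatment rate of 20 per 100 person-years.
- Same true rate off treatment: observed on/off rates are 15.0/6.7 (D = 4), 20.0/11.7 (D = 8) and 20.0/15.0 (D = 12).
- True off-treatment rate twice as high: 15.0/13.3, 20.0/23.3 and 20.0/30.0.

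**The case against.** A reader might infer that flare rates must fall after treatment by construction. The documents do not support that. Detection falls; the observed rate depends on true rates and durations that the documents do not give. In the last illustration above, the observed rate rises for 8- and 12-week flares.

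A reader might also infer that off-treatment safety as a whole will look better than it is. That goes too far. Under section 7.5.2, staff record events they learn of between visits, so only silent laboratory events are at issue. The same section describes capture by interview, and grading outside the modified WHO system is left to a manual that is not among the documents. How far silent ALT values enter the adverse event rate is therefore not established.

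Further points stand. None of the 13 summaries in section 8.1.1 names ALT flare, splits weeks 0-48 from 48-96, or compares on with off treatment; that comparison is an inference from sections 2.1 and 2.2.1. Sections 6.11.3 and 6.12.3 provide for elevations lasting more than 12 weeks and at least 24 weeks, where the bias is small or absent. If withdrawal flares come early, they fall in weeks 48-60, which are watched about as closely as treatment. And this is a descriptive single-arm pilot of 40 participants.

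It could also be said that the plan already has visit-based ALT summaries. Section 8.1.2.2 describes changes from baseline with means, medians and spread, and sections 2.3.1 and 2.3.2 give percentages below 45/30 and 30/20 U/L at weeks 48 and 96. None of these shows how many participants reached flare-level ALT at each visit, so this part of the objection does not meet the point.

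**Conclusion.** The concern holds in limited form. To the extent that silent ALT flares enter the adverse event data, their person-year rate after week 60 is biased downward relative to weeks 0-48. Under uniform onset, the under-detection over the whole off-treatment period is more than two-fold for 4-week flares, 1.2-fold at 16 weeks and nil from 24 weeks. Under the cumulative windows that the plan names, the dilution is milder, about 0.72 to 0.88 for 4- to 12-week flares at equal true rates.

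These sizes rest on assumed durations, uniform onset and silent flares. The visit gaps and the direction of the bias for flares shorter than the longest gap come from the documents. The point is one of reporting: it does not touch symptomatic events or the efficacy analysis, and it does not show that off-treatment safety will be misjudged overall.

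**What to change.** In section 8.1.1, add that laboratory-detected ALT flares are reported as the proportion of tested participants above the limits of sections 6.11 and 6.12 at each scheduled visit, visit by visit. Exclude unscheduled retests, since they occur only in participants already found above the limit. Do not pool across visits, because a long flare would be counted repeatedly, and more often where panels are close together. Sections 6.11.1 and 6.12.1 differ on whether a value exactly at the limit counts, so state the convention used in the table.

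State that on- versus off-treatment safety is not to be read from person-year rates of these events. If such a rate is kept, split it into weeks 0-48, 48-60 and 60-96, and label the last figure a lower bound with onset known only to within the visit gap. Symptomatic events keep their person-year rate.

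Do not restrict the off-treatment analysis to weeks 48-60. That would discard 36 of 48 weeks and leave about 40 × 12 × 7/365.25 = 9.2 person-years, or about 1.8 events at the assumed 20 per 100 person-years.

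The cost is a few sentences and one extra table from data already collected, with no new visits. The visit-level figures measure prevalence rather than incidence, and the table should say so.
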